## 12. PLANS FOR DISSEMINATING AND COMMUNICATING STUDY RESULTS

The study protocol synopsis, study status, and report(s) will be included in regulatory communications in line with the risk management plan, Benefit-Risk Evaluation Report, and other regulatory milestones and requirements.

Study results will be published following the International Committee of Medical Journal Editors recommendations, [\[R13-5418\]](#) and communication in appropriate scientific venues (e.g., the International Society for Pharmacoepidemiology) will be considered.

When reporting results of this study, the appropriate Strengthening the Reporting of Observational Studies in Epidemiology checklist [\[R11-4902\]](#) will be followed.

## **ANNEX 1. LIST OF STAND-ALONE DOCUMENTS**

None

## **ANNEX 2. ENCEPP CHECKLIST FOR STUDY PROTOCOLS**

EUROPEAN MEDICINES AGENCY  
SCIENCE MEDICINES HEALTH

European Network of Centres for  
Pharmacoepidemiology and  
Pharmacovigilance

Doc.Ref. EMA/540136/2009

## **ENCePP Checklist for Study Protocols (Revision 2, amended)**

Adopted by the ENCePP Steering Group on 14/01/2013

The European Network of Centres for Pharmacoepidemiology and Pharmacovigilance (ENCePP) welcomes innovative designs and new methods of research. This Checklist has been developed by ENCePP to stimulate consideration of important principles when designing and writing a pharmacoepidemiological or pharmacovigilance study protocol. The Checklist is intended to promote the quality of such studies, not their uniformity. The user is also referred to the ENCePP Guide on Methodological Standards in Pharmacoepidemiology which reviews and gives direct electronic access to guidance for research in pharmacoepidemiology and pharmacovigilance.

For each question of the Checklist, the investigator should indicate whether or not it has been addressed in the study protocol. If the answer is "Yes", the page number(s) of the protocol where this issue has been discussed should be specified. It is possible that some questions do not apply to a particular study (for example in the case of an innovative study design). In this case, the answer 'N/A' (Not Applicable) can be checked and the "Comments" field included for each section should be used to explain why. The "Comments" field can also be used to elaborate on a "No" answer.

This Checklist should be included as an Annex by marketing authorisation holders when submitting the protocol of a non-interventional post-authorisation safety study (PASS) to a regulatory authority (see the Guidance on the format and content of the protocol of non-interventional post-authorisation safety studies). Note, the Checklist is a supporting document and does not replace the format of the protocol for PASS as recommended in the Guidance and Module VIII of the Good pharmacovigilance practices (GVP).

**Study title:**

Drug Utilisation Study for Olodaterol

**Study reference number:**

1222.53

| Section 1: Milestones                | Yes                          | No                | N/A                          | Page Number(s) |
|---|-------------------------------------|--------------------------|-------------------------------------|-----------------------|
| 1.1 Does the protocol specify timelines for |                                     |                          |                                     |                       |
| 1.1.1 Start of data collection  |  |  |             | 12                    |
| 1.1.2 End of data collection    |  |  |             | 12                    |
| 1.1.3 Study progress report(s)              |             |  |  | 12                    |
| 1.1.4 Interim progress report(s)            |  |  |             | 12                    |
| 1.1.5 Registration in the EU PAS register   |             |  |             | 12                    |
| 1.1.6 Final report of study results.        |  |  |             | 12                    |

Comments:

Timing of PAS registration has not yet been determined.

| Section 2: Research question   | Yes                          | No                           | N/A                          | Page Number(s) |
|---|-------------------------------------|-------------------------------------|-------------------------------------|-----------------------|
| 2.1 Does the formulation of the research question and objectives clearly explain:   |                                     |                                     |                                     |                       |
| 2.1.1 Why the study is conducted? (e.g. to address an important public health concern, a risk identified in the risk management plan, an emerging safety issue) |  |             |             | 13                    |
| 2.1.2 The objective(s) of the study?  |  |             |             | 14                    |
| 2.1.3 The target population? (i.e. population or subgroup to whom the study results are intended to be generalised)   |  |             |             | 15                    |
| 2.1.4 Which formal hypothesis(-es) is (are) to be tested?   |             |             |  |                       |
| 2.1.5 If applicable, that there is no a priori hypothesis?   |             |  |             |                       |

Comments:

there is no a priori hypothesis and the objective is to measure the relative frequency of off label use among olodaterol and comparator

| Section 3: Study design  | Yes                          | No                | N/A                          | Page Number(s) |
|---|-------------------------------------|--------------------------|-------------------------------------|-----------------------|
| 3.1 Is the study design described? (e.g. cohort, case-control, randomised controlled trial, new or alternative design)  |  |  |             | 15                    |
| 3.2 Does the protocol specify the primary and secondary (if applicable) endpoint(s) to be investigated?   |  |  |             | 28                    |
| 3.3 Does the protocol describe the measure(s) of effect? (e.g. relative risk, odds ratio, deaths per 1000 person-years, absolute risk, excess risk, incidence rate ratio, hazard ratio, number needed to harm (NNH) per year) |             |  |  |                       |

Comments:

1 Date from which information on the first study is first recorded in the study dataset or, in the case of secondary use of data, the date from which data extraction starts.

2 Date from which the analytical dataset is completely available.

| Section 4: Source and study populations   | Yes                          | No                | N/A                          | Page Number(s) |
|--|-------------------------------------|--------------------------|-------------------------------------|-----------------------|
| 4.1 Is the source population described?  |  |  |             | 18                    |
| 4.2 Is the planned study population defined in terms of:   |  |  |             | 18
18
19
18  |
| 4.2.1 Study time period?   |  |  |             |                       |
| 4.2.2 Age and sex?   |  |  |             |                       |
| 4.2.3 Country of origin?   |  |  |             |                       |
| 4.2.4 Disease/indication?  |             |  |  |                       |
| 4.2.5 Co-morbidity?  |             |  |  |                       |
| 4.2.6 Seasonality?   |             |  |  |                       |
| 4.3 Does the protocol define how the study population will be sampled from the source population? (e.g. event or inclusion/exclusion criteria) |  |  |             | 19                    |

Comments:

|  |
|--|
|  |
|--|

| Section 5: Exposure definition and measurement   | Yes                          | No                           | N/A                          | Page Number(s) |
|---|-------------------------------------|-------------------------------------|-------------------------------------|-----------------------|
| 5.1 Does the protocol describe how exposure is defined and measured? (e.g. operational details for defining and categorising exposure)  |  |             |             | 19                    |
| 5.2 Does the protocol discuss the validity of exposure measurement? (e.g. precision, accuracy, prospective ascertainment, exposure information recorded before the outcome occurred, use of validation sub-study) |             |             |  |                       |
| 5.3 Is exposure classified according to time windows? (e.g. current user, former user, non-use)   |             |             |  |                       |
| 5.4 Is exposure classified based on biological mechanism of action and taking into account the pharmacokinetics and pharmacodynamics of the drug?   |             |  |             |                       |
| 5.5 Does the protocol specify whether a dose-dependent or duration-dependent response is measured?  |             |             |  |                       |

Comments:

|  |
|--|
| This DUS is limited to characterizing the subjects on and before first use; exposure group of interest consists of all new users |
|--|

| Section 6: Endpoint definition and measurement  | Yes                          | No                | N/A               | Page Number(s) |
|--|-------------------------------------|--------------------------|--------------------------|-----------------------|
| 6.1 Does the protocol describe how the endpoints are defined and measured?   |  |  |  | 20                    |
| 6.2 Does the protocol discuss the validity of endpoint measurement? (e.g. precision, accuracy, sensitivity, specificity, positive predictive value, prospective or retrospective ascertainment, use of validation sub-study) |  |  |  | 19-22                 |

Comments:

|  |
|--|
|  |
|--|

| Section 7: Confounders and effect modifiers   | Yes               | No                | N/A                          | Page Number(s) |
|--|--------------------------|--------------------------|-------------------------------------|-----------------------|
| 7.1 Does the protocol address known confounders?
(e.g. collection of data on known confounders, methods of controlling for known confounders) |  |  |  |                       |
| 7.2 Does the protocol address known effect modifiers?
(e.g. collection of data on known effect modifiers, anticipated direction of effect)    |  |  |  |                       |

Comments:

|  |
|--|
| Confounding and effect modification is not expected to be an issue for this descriptive study. |
|--|

| Section 8: Data sources  | Yes                          | No                | N/A               | Page Number(s) |
|---|-------------------------------------|--------------------------|--------------------------|-----------------------|
| 8.1 Does the protocol describe the data source(s) used in the study for the ascertainment of:   |                                     |                          |                          |                       |
| 8.1.1 Exposure? (e.g. pharmacy dispensing, general practice prescribing, claims data, self-report, face-to-face interview, etc.)  |  |  |  | 19                    |
| 8.1.2 Endpoints? (e.g. clinical records, laboratory markers or values, claims data, self-report, patient interview including scales and questionnaires, vital statistics, etc.) |  |  |  | 20                    |
| 8.1.3 Covariates?   |  |  |  | 23                    |
| 8.2 Does the protocol describe the information available from the data source(s) on:  |                                     |                          |                          |                       |
| 8.2.1 Exposure? (e.g. date of dispensing, drug quantity, dose, number of days of supply prescription, daily dosage, prescriber)   |  |  |  | 19                    |
| 8.2.2 Endpoints? (e.g. date of occurrence, multiple event, severity measures related to event)  |  |  |  | 20                    |
| 8.2.3 Covariates? (e.g. age, sex, clinical and drug use history, co-morbidity, co-medications, life style, etc.)  |  |  |  | 23                    |
| 8.3 Is a coding system described for:   |                                     |                          |                          |                       |
| 8.3.1 Diseases? (e.g. International Classification of Diseases (ICD)-10)  |  |  |  | 21-22                 |
| 8.3.2 Endpoints? (e.g. Medical Dictionary for Regulatory Activities (MedDRA) for adverse events)  |  |  |  | 21-22                 |
| 8.3.3 Exposure? (e.g. WHO Drug Dictionary, Anatomical Therapeutic Chemical (ATC) Classification System)   |  |  |  | 31                    |
| 8.4 Is the linkage method between data sources described? (e.g. based on a unique identifier or other)  |  |  |  | 29                    |

Comments:

|  |
|--|
|  |
|--|

| Section 9: Study size and power                  | Yes                          | No                | N/A               | Page Number(s) |
|---|-------------------------------------|--------------------------|--------------------------|-----------------------|
| 9.1 Is sample size and/or statistical power calculated? |  |  |  | 35                    |

Comments:

|  |
|--|
|  |
|--|

| Section 10: Analysis plan                             | Yes                          | No                | N/A                          | Page Number(s) |
|---|-------------------------------------|--------------------------|-------------------------------------|-----------------------|
| 10.1 Does the plan include measurement of excess risks?             |             |  |  |                       |
| 10.2 Is the choice of statistical techniques described?             |  |  |             | 36                    |
| 10.3 Are descriptive analyses included?                             |  |  |             | 36                    |
| 10.4 Are stratified analyses included?                              |  |  |             | 36                    |
| 10.5 Does the plan describe methods for adjusting for confounding?  |             |  |  |                       |
| 10.6 Does the plan describe methods addressing effect modification? |             |  |  |                       |

Comments:

|  |
|--|
| Confounding and effect modification are not relevant to this descriptive study |
|--|

| Section 11: Data management and quality control   | Yes                          | No                           | N/A               | Page Number(s) |
|---|-------------------------------------|-------------------------------------|--------------------------|-----------------------|
| 11.1 Is information provided on the management of missing data?   |  |             |  | 35                    |
| 11.2 Does the protocol provide information on data storage? (e.g. software and IT environment, database maintenance and anti-fraud protection, archiving) |  |  |  | 38                    |
| 11.3 Are methods of quality assurance described?  |  |             |  | 38                    |
| 11.4 Does the protocol describe possible quality issues related to the data source(s)?  |             |  |  |                       |
| 11.5 Is there a system in place for independent review of study results?  |             |  |  |                       |

Comments:

|  |
|--|
| 
11.1-11.3 This is a core protocol that will be implemented by multiple research institution that are qualified and have available staffing at the time of study initiation, i.e. after EMA review, olodaterol is launched. At that time the specifics of data management for each data source and corresponding research institution, including quality control and data security, can be specified.
 
11. 5 To date no advisory board is planned.
 |
|--|

| Section 12: Limitations                     | Yes                          | No                | N/A                          | Page Number(s) |
|---|-------------------------------------|--------------------------|-------------------------------------|-----------------------|
| 12.1 Does the protocol discuss:                           |                                     |                          |                                     |                       |
| 12.1.1 Selection biases?                                  |             |  |  |                       |
| 12.1.2 Information biases?                                |                                     |                          |                                     |                       |
| (e.g. anticipated direction and magnitude of such biases, |  |  |             | 37-38                 |

| Section 12: Limitations   | Yes                          | No                | N/A               | Page Number(s) |
|--|-------------------------------------|--------------------------|--------------------------|-----------------------|
| validation sub-study, use of validation and external data, analytical methods)   |                                     |                          |                          |                       |
| 12.2 Does the protocol discuss study feasibility? (e.g. sample size, anticipated exposure, duration of follow-up in a cohort study, patient recruitment) |  |  |  | 37-38                 |
| 12.3 Does the protocol address other limitations?  |  |  |  | 37-38                 |

Comments:

|  |
|--|
|  |
|--|

| Section 13: Ethical issues  | Yes                          | No                           | N/A               | Page Number(s) |
|--|-------------------------------------|-------------------------------------|--------------------------|-----------------------|
| 13.1 Have requirements of Ethics Committee/Institutional Review Board approval been described? |  |             |  | 40                    |
| 13.2 Has any outcome of an ethical review procedure been addressed?                            |             |  |  |                       |
| 13.3 Have data protection requirements been described?   |             |  |  | 35                    |

Comments:

For this core protocol, the data protection procedures will be consistent with local procedures and more details will be added into data source-specific study documents

| Section 14: Amendments and deviations   | Yes                          | No                | N/A               | Page Number(s) |
|--|-------------------------------------|--------------------------|--------------------------|-----------------------|
| 14.1 Does the protocol include a section to document future amendments and deviations? |  |  |  | 11                    |

Comments:

|  |
|--|
|  |
|--|

| Section 15: Plans for communication of study results                                 | Yes                          | No                | N/A               | Page Number(s) |
|---|-------------------------------------|--------------------------|--------------------------|-----------------------|

### ANNEX 3. EVALUATION OF COPD SEVERITY IN AUTOMATED HEALTH DATABASES

Annex Table 3:1 Published definitions of COPD severity in studies conducted in automated health databases

| Reference, Severity Criteria  | COPD Severity  |  |   |
|---|--|--|---|
|   | Mild   | Moderate   | Severe  |
| Integrated Primary Care Information Project, Netherlands [P11-13226]   |  |  |   |
| 
With spirometry data, used GOLD criteria [P13-02399]
 
Without spirometry, used methods of Curkendall et al., [R09-0579] Eisner et al., [R13-1392] and Soriano et al. [R08-1492]
  | At initial COPD symptoms   | At least 2 prescriptions of bronchodilators of the same drug class with a maximum interval of 6 months in 1 year | 
Severe:
 
 
• Hospitalisation for COPD, or
 
• Third course of antibiotics for respiratory infection in 1 year, or
 
• Second course of systemic corticosteroids for COPD exacerbation in 1 year
 
 
Very severe:
 
 
• Oxygen therapy, or
 
• Scheduled for lung transplant
 
 |
| Saskatchewan Health, Canada [R09-0579]   |  |  |   |
| 
Case-control study to find severity marker variables, using:
 
 
• Pre-existing chronic conditions
 
• Recent acute conditions
 
• Recent high use of bronchodilators
 
 
Specific components of the above are detailed in the article's appendix
 | Patients ranked into 5 quintiles by likelihood of COPD hospitalisation, from conditional logistic regression model |  | 
Factors in previous 180 days associated with severe COPD:
 
 
• Emphysema
 
• Recent nebuliser use
 
• Home oxygen therapy
 
• Corticosteroid use
 
• Frequent bronchodilator use
 
• Pneumonia
 
• Previous COPD exacerbation
 
   |

Proprietary confidential information © 2014 Boehringer Ingelheim International GmbH or one or more of its affiliated companies

Annex Table 3:1 (con't) Published definitions of COPD severity in studies conducted in automated health databases

| Reference, Severity criteria   | COPD Severity              |   |   |
|--|----------------------------|---|---|
|  | Mild                       | Moderate  | Severe  |
| General Practice Research Database, United Kingdom Soriano [R08-1492] |                            |   |   |
| Severity based only on drug data   | At first diagnosis of COPD | At least 2 prescriptions of the same COPD drug within 6 months, using data on inhaled or oral bronchodilators, xanthines, cromones, steroids, or combinations | 
 
• Oxygen therapy, or
 
• Nebuliser therapy
 
 |

COPD = Chronic Obstructive Pulmonary Disease; GOLD = Global Initiative for Chronic Obstructive Lung Disease.

1 This database is now known as Clinical Practice Research Datalink.

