### 9.3.3.4 Definition of COPD severity

Severity of COPD will be evaluated among new users of olodaterol and indacaterol that have a recorded diagnosis of COPD before the index date. Severity of COPD will be evaluated at the index date by a modified version of the algorithm developed by Verhamme and colleagues [[P11-13226](#)] (see [Table 7](#)).

Table 7 Definition criteria of COPD severity

| Severity of COPD | Definition   |
|-------------------------|---|
| Mild                    | Less than 2 dispensings of the same COPD drug class with a maximum interval of 6 months in the 12 months before the index date.   |
| Moderate                | Regular bronchodilator treatment, defined as having at least 2 dispensings of the same COPD drug class with a maximum interval of 6 months in the 12 months before the index date   |
| Severe                  | Occurrence of at least one of the following events in the year before the index date: 
 
• Hospitalisation for COPD
 
• Recorded diagnosis of pneumonia
 
• Third course of antibiotics for respiratory tract infections
 
• Second course of systemic corticosteroids for the treatment of COPD exacerbation
 
 |
| Very severe             | Occurrence of at least one of the following events in the year before the index date unless other time period is specified: 
 
• Dispensed oxygen therapy
 
• Dispensed nebuliser therapy
 
• Diagnosis of emphysema at any time before the index date
 
   |

COPD = Chronic Obstructive Pulmonary Disease.

Sources: modified from Verhamme et al., 2012 [[P11-13226](#)]; Soriano et al., 2001 [[R08-1492](#)]; and Curkendall et al., 2006. [[P07-09136](#)]

1 Severity criteria also included in definition from Soriano et al., 2001. [[R08-1492](#)]

2 Severity criteria also included in definition from Curkendall et al., 2006. [[P07-09136](#)]

The use of antibiotics and oral corticosteroids and hospitalisations for COPD haven been used by other authors as markers of severity of COPD exacerbations. [[P12-09396](#)] [[P12-09395](#)] [[P12-14293](#)]

The operational definitions to be applied when assessing the severity of COPD are as follows:

- Same-class bronchodilators. The following bronchodilators classes will be considered (see [Annex Table 4:2](#)):

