5.3.3 Severity of COPD

Severity of COPD will be evaluated among new users of olodaterol and indacaterol that are aged 40 years or older and have a recorded diagnosis of COPD (with or without a diagnosis of asthma) ever before or up 30 days after the index date. The population aged 40 years or older is considered the most likely to have COPD and is frequently selected in studies to evaluate medication use among patients with COPD [[P07-07347](#), [P11-13226](#), [P07-09136](#)]. Patients aged 39 years or younger with a diagnosis of COPD will still be considered as

Proprietary confidential information © 2017 Boehringer Ingelheim International GmbH or one or more of its affiliated companies

having COPD and described separately if there are at least 5 patients in each COPD severity category. Definitions shown in [Table 8](#) will be adapted to the characteristics and data availability in each data source; database-specific specifications have been described in [Section 9.2](#). The four severity categories will be mutually exclusive, and patients that fulfil criteria for more than one category will be classified as being in the more severe category.

Table 8 Definition criteria of COPD severity (adapted primarily from Verhamme et al., 2012 [[P11-13226](#)])

Severity of COPD	Definition
Mild	Less than two prescriptions/dispensings of drugs for obstructive airways disease of the same class in any 6-month interval in the 12 months before the index date (i.e., 0 or 1 prescriptions/dispensings of the same COPD drug class in the 12 months before the index date, or if ≥ 2 prescriptions/dispensings, these have to be more than 6 months apart)
Moderate	Regular bronchodilator treatment, defined as having at least two prescriptions/dispensings of the same COPD drug class with an interval of ≤ 6 months in the 12 months before the index date ^{1,2}
Severe	Occurrence of at least one of the following events in the 12 months before the index date: 
 • Hospitalisation for COPD exacerbation¹ • At least two COPD exacerbations without hospitalisation, where COPD exacerbation is defined by any of the following³: 
 • A course of antibiotics for lower respiratory tract infection (acute bronchitis or pneumonia)¹ • A course of systemic corticosteroids for the treatment of COPD exacerbation¹ • A diagnoses of COPD exacerbation without hospitalisation

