Very severe	Occurrence of at least one of the following events in the 12 months before the index date unless another time period is specified: 
 • Dispensed oxygen therapy^{1,2} • Dispensed nebuliser therapy^{1,2} • Diagnosis of emphysema at any time before the index date¹

COPD = Chronic Obstructive Pulmonary Disease.

- 1 Severity criteria also included in definition from Curkendall et al., 2006 [[P07-09136](#)].
- 2 Severity criteria also included in definition from Soriano et al., 2001 [[R08-1492](#)].
- 3 Severity criteria modified to align with the Global Initiative for Chronic Obstructive Lung Disease (GOLD) 2016 definition for severity categories C and D [[P16-00121](#)]. If two or more of these criteria occur within a 21-day time period, they will be considered part of the same exacerbation episode and counted only once. If one or more of these criteria occur within a 21-day period of a hospitalisation for COPD, this will be considered part of the same “COPD exacerbation with hospitalisation” episode.

Sources: modified from Verhamme et al., 2012 [[P11-13226](#)]; Soriano et al., 2001 [[R08-1492](#)]; Curkendall et al., 2006 [[P07-09136](#)]; and GOLD, 2016 [[P16-00121](#)].

Because data on hospitalisations are not available in the IMS RWE LPD database, COPD severity will not be described in this database.

The proposed operational definitions to be applied when assessing the severity of COPD are as follows:

- Same-class “drugs for obstructive airways disease”: medications listed in [Annex Table 1-6](#) will be identified through prescriptions/dispensings for the list of medications of interest recorded in the database within 12 months before or on the index date and classified into one of the following drug classes:
 - Bronchodilators: inhaled short-acting muscarinic antagonists (SAMAs), inhaled LAMAs, inhaled short-acting beta2-agonists (SABAs), inhaled LABAs, and fixed combinations of SABAs and SAMAs
 - Inhaled glucocorticosteroids: ICS alone, fixed combinations of SABAs and ICSs, and fixed combinations of LABAs and ICSs
 - Systemic glucocorticosteroids
 - Systemic beta2-agonists
 - Xanthines
 - Roflumilast
- Hospitalisation for COPD exacerbation: an inpatient (primary or secondary discharge) code for COPD (ICD-10 codes: J41-J44), acute bronchitis (ICD-10 codes: J20, J21, J22, J40), or pneumonia (ICD-10 codes J09, J18) within 12 months before or on the index date.

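### SAP 5.3.3: one exacerbation with systemic steroids dispensed on two dates within 21 days makes an otherwise Mild patient Moderate, under a criterion labelled as bronchodilator treatment

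*Protocol*

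**What the plan says.** **Sources.** The SAP 5.3.3 severity table (Table 8) is headed "Definition criteria of COPD severity (adapted primarily from" the Dutch study, and its source line names further sources. Protocol Annex 3 gives the Dutch Moderate level as "At least 2 prescriptions of bronchodilators of the same drug class with a maximum interval of 6 months in 1 year". For the UK general practice study, which is also footnoted to the SAP's Moderate row, Annex 3 gives "At least 2 prescriptions of the same COPD drug within 6 months, using data on inhaled or oral bronchodilators, xanthines, cromones, steroids, or combinations".

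**Mild and Moderate.** SAP Table 8 defines Moderate as "Regular bronchodilator treatment, defined as having at least two prescriptions/dispensings of the same COPD drug class with an interval of ≤ 6 months". Its Mild row covers "0 or 1 prescriptions/dispensings of the same COPD drug class in the 12 months before the index date", or repeat dispensings more than 6 months apart.

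**Class list.** The operational definitions in SAP 5.3.3 say that drugs are "classified into one of the following drug classes". One of the six classes is systemic glucocorticosteroids. Protocol 9.3.3.4 has the same entry under the heading "Same-class bronchodilators. The following bronchodilators classes will be considered".

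**Severe.** Without hospitalisation, SAP Table 8 requires at least two exacerbations in 12 months. A course of systemic steroids is one marker of an exacerbation. Footnote 3 says of markers falling within 21 days that "they will be considered part of the same exacerbation episode and counted only once".

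**The concern.** The same steroid records can enter the severity rule twice. For Severe they are merged into episodes. For Mild versus Moderate they are counted as separate dispensings, with no merging. One acute episode supplied on two dates can then be read as regular treatment, in a patient who received no bronchodilator before the index date.

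The category would then depend on how many times the pharmacy dispensed. Of two patients with one steroid-treated episode each, the one supplied once stays Mild and the one supplied twice becomes Moderate. Description of baseline characteristics is a primary objective, and severity is one of those characteristics for patients with COPD. At stake is the split between Mild and Moderate in that description.

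**Working it through.** The plan gives no figure to reproduce, so the check applies its rules to a constructed patient. The patient has COPD, no hospitalisation, antibiotics, other exacerbation record, oxygen, nebuliser or emphysema, no other class repeated within 6 months, and one or two systemic steroid dispensings.

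**Inputs**
- Moderate: two dispensings of one class at most 6 months apart (SAP Table 8); 6 months taken as 183 days.
- Severe: at least two non-hospitalised exacerbations (SAP Table 8).
- Episode: records within 21 days of the first record are one exacerbation (SAP 5.3.3).
- Course: less than 7 days from end of supply to the next dispensing (SAP 5.3.3 and Protocol 9.3.3.4).
- Days of supply: not in the documents; 5, 7 and 14 days assumed.

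**SAP rule.** Let g be the days between the two dispensing dates. The Moderate test is met if g ≤ 183. The two records are one episode, so not Severe, if g ≤ 21. Gaps of 3, 6, 10, 13, 14, 20, 21, 22, 28, 60 and 200 days were tried with each supply:

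| Systemic steroid dispensings | SAP as written | SAP, bronchodilators only |
|---|---|---|
| One | Mild | Mild |
| Two, 3 to 21 days apart | Moderate | Mild |
| Two, 22 or more days apart | Severe | Severe |

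In these cases the steroid class changes the result only where both dispensings belong to one episode.

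**Protocol rule.** Protocol 9.3.3.4 makes a second steroid course Severe and has no 21-day merge. With supply s, the two dispensings are one course if g − s < 7, that is g ≤ s + 6: up to day 11, 13 or 20 for supplies of 5, 7 or 14 days. Up to that day the protocol gives Moderate; after it, Severe. The protocol therefore has the same feature over a shorter gap. The SAP's merge extends it to day 21: with a 5-day supply, gaps of 12 to 21 days were Severe under the protocol and are Moderate under the SAP.

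**Long supplies.** Assume 30-day supplies refilled every 30 days. The gap after end of supply is 30 − 30 = 0 days, below 7, so a year of treatment is one course. Read by courses, this is one exacerbation and not Severe. Read by dispensing dates, 30 > 21, so it is more than one episode. As written, such a patient is at least Moderate. If the steroid class is deleted and nothing else repeats, the course reading makes the patient Mild.

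**Size, illustration only.** Suppose 10–30% of otherwise Mild patients had exactly one steroid-treated episode, and 10–30% of those episodes were dispensed on two dates within 21 days. The share moved is then 0.10 × 0.10 = 0.01 to 0.30 × 0.30 = 0.09. Neither input has a basis in the documents.

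**The case against.** The strongest reply is that counting steroids follows a cited source. The UK study is footnoted to the Moderate row and its rule names steroids. Annex 3 adds that the Dutch study, where it lacked spirometry, itself drew on the UK methods. A reader might infer that the SAP contradicts its source algorithm, or that the SAP introduced the steroid class. Neither is supported: the departure is from the primary source only, and the protocol already lists the class. What remains is the double use. The UK definition, as Annex 3 summarises it, rests on drug data alone and has no exacerbation level; the SAP adds one that uses the same drug group.

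The class list is also explicit and programmable, and the SAP renames it as drugs for obstructive airways disease, so rewording the Moderate label might seem enough. That would settle the label but leave one episode counted as two dispensings.

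The documents do not show that Mild is the correct category for a patient with a steroid-treated exacerbation; corticosteroid use is a severity marker elsewhere in them. This stands. The point is that one episode should not change category with the number of dispensing dates.

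Outright deletion of the class is tempting but not safe as it stands. It could move the continuous steroid user above to Mild, and it would leave inhaled steroids alone and roflumilast under a bronchodilator label.

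Finally, part of the specification cannot be seen. SAP Section 9.2, with the database-specific definitions, is not in the available text. The exacerbation criterion uses country-specific steroid lists, whereas the SAP's medication annex gives all of H02AB, so full overlap of the two sets of dispensings is not established. SAP 7.1.3 will show the criteria met within each category, but it does not say that Moderate will be split by drug class.

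**Conclusion.** The point holds as an inconsistency between label and class list in both documents, with a specific artefact in the SAP: one exacerbation with steroids dispensed on two dates within 21 days is too little for Severe but enough for Moderate. It applies only when no other class is repeated within 6 months and no Severe or Very severe criterion is met.

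The number of patients is unknown. The 1–9% range is arithmetic on assumed inputs and should not be cited as an estimate. A reader might also infer that the shift is concentrated among LABA-naïve patients. The documents do not show this: that stratum means only no LABA in the 3 months before the index date (Protocol 9.2.3) and says nothing about short-acting, muscarinic or inhaled steroid use.

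The consequence is limited to the descriptive severity distribution in PHARMO and Denmark, since SAP 5.3.3 does not describe severity in the French database. Off-label prevalence is unaffected because SAP 5.1 classifies by age and diagnosis. This is a minor, optional improvement. The results at 22 days or more rest on the 5-, 7- and 14-day supplies tried.

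**What to change.** 1. In SAP 5.3.3, state that systemic steroid dispensings belonging to one exacerbation episode under the SAP's own 21-day rule count once for Mild versus Moderate. Dispensings in different episodes still count separately, so the continuous user with 30-day refills is not pushed to Mild. Alternatively, remove the class from that rule and state how continuous steroid users are classified.
2. Align the Moderate label with the class list, either by naming it as regular COPD drug treatment or by restricting the list to match the label.
3. State which source the Moderate row follows on this point, and record the change in SAP Section 4.
4. Report the severity distribution with and without the systemic steroid class, so that the size of the effect is seen.

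The cost is a few lines of text and program and one extra table. No new data are needed. The Moderate count becomes slightly lower.
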